Dose Regimen of MDMA

Experimental Session	Initial Dose	Supplemental Dose*	Min-Max Cumulative Dose
1	80 mg	40 mg	80 mg to 120 mg
2	80 or 120 mg	40 or 60 mg	80 mg to 180 mg
3	80 or 120 mg	40 or 60 mg	80 mg to 180 mg
	7	Total Cumulative Dose	240 mg to 480 mg

^{*} Unless tolerability issues emerge with the first dose or it is refused by the participant.

Protocol Objective

The overall objective of this study is to use standard clinical measures to explore the safety and effectiveness of MDMA-assisted therapy with a flexible dose of MDMA in reducing PTSD and associated symptoms.

Primary Objective

The primary objective of this study is to evaluate the effectiveness of MDMA-assisted therapy for PTSD, as measured by the reduction in PCL-5 total score from Visit 3 to Visit 16.

Secondary Objective

The key secondary objective of this study is to evaluate the effectiveness of MDMA-assisted therapy for PTSD in functional impairment, as measured by the mean change in Sheehan Disability Scale (SDS) item scores from Visit 3 to Visit 16.

Safety Objectives

The overall safety objective is to assess severity, incidence and frequency of Adverse Events (AEs), Treatment Emergent AEs (TEAEs), AEs of Special Interest (AESIs), and Serious Adverse Events (SAEs), concomitant medication use, suicidal ideation and behavior, and vital signs to support the package insert for MDMA-assisted therapy. The following safety objectives will evaluate the safety of MDMA-assisted therapy:

- 1. Assess incidence of AEs during Experimental Sessions that may be indicative of a medical complication of the Investigational Medicinal Product (IMP) such as clinical signs and symptoms of chest pain, shortness of breath, or neurological symptoms or any other signs or symptoms that prompt additional vital sign measurements
- 2. Assess incidence of AEs by severity
- 3. Assess incidence of TEAEs by severity
- 4. Assess incidence of TEAEs by severity reported during an Experimental Session, 1 day, and 2 days after IMP administration
- 5. Assess incidence of AESIs, defined as AEs specified in the protocol related to cardiac function, suicidality, and abuse liability
- 6. Assess incidence of AEs by severity categorized as leading to discontinuation of IMP, resulting in death or hospitalization, and continuing at Study Termination
- 7. Assess incidence of SAEs
- 8. Assess incidence of concomitant medications taken during an Experimental Session, 1 day, and 2 days after IMP administration

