10.0 Safety

10.1 Adverse Events, Serious Adverse Events, Adverse Events of Special Interest and Other **Safety Reporting**

MAPPUSX Protocol

The investigator and any qualified designees are responsible for detecting, documenting, and recording events that meet the definition of an Adverse Event (AE), Serious Adverse Event (SAE), or Adverse Event of Special Interest (AESI), and remain responsible for following up on all AEs.

AEs will be reported by the participant (or, when appropriate, by a caregiver, surrogate, or the participant's legally authorized representative). The collection period of AEs is from the time of signed ICF until the completion of the study termination visit (+/- 2 days). Medical occurrences that begin before the start of Visit 0, but after obtaining informed consent may be recorded as medical history or a current medical conditions, unless the event occurs as a result of a study requirement in which case the event would be reported as an AE. All AEs should be recorded regardless of the cause of the event, whether the event is deemed positive, negative or neutral by the investigator, reporter or qualified designee. The investigator will elicit information through non-leading open-ended questioning and examination of the participant about the occurrence of the AE. For each event, the following information will be recorded in the participant's record and transcribed into the AE section of the eCRF and SAE form when appropriate according to the instructions below:

- Classification of the event: serious or non-serious
- Classification of the event as an adverse event of special interest (AESI)
- Description of signs and/or symptoms. Whenever possible, the specific diagnosis for the event will be recorded. If a diagnosis cannot be made, each sign or symptom will be recorded separately (e.g., nausea and vomiting would be recorded as two separate events).
- Severity of event: mild, moderate or severe
- Relationship to study medication: related or not related
- Action taken with study medication: dose maintained, dose not changed, dose reduced, interruption of dose, drug withdrawn/discontinued, unknown, or not applicable
- Adverse event outcome: resolved without sequelae, resolved with sequelae (describe sequelae), resolving, not resolved, fatal, or unknown (lost to follow-up)
- Event onset date. If a laboratory event is reported as an AE, record the start date as the date of collection of the first lab sample that shows the change.

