- Event stop date: date the event resolved

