This sub-study will include all participants enrolled and treated at select study sites. No formal analysis is planned to support this objective due to small sample size. However, case reports and AEs collected on the night of the Experimental Session will be evaluated to support feasibility. These reports will be used to explore feasibility of expanding the sub-study to include additional clinical sites and to support generalizability of potentially delivering this treatment to varied treatment settings post-approval.

References

- 1. Yehuda, R., et al., *Post-traumatic stress disorder*. Nat Rev Dis Primers, 2015. 1: p. 15057.
- 2. APA, Clinical practice guideline for the treatment of posttraumatic stress disorder (PTSD) in adults. 2017.
- 3. Burg, M.M. and R. Soufer, *Post-traumatic Stress Disorder and Cardiovascular Disease*. Curr Cardiol Rep, 2016. **18**(10): p. 94.
- 4. Koenen, K.C., et al., *Posttraumatic stress disorder in the World Mental Health Surveys.* Psychol Med, 2017. **47**(13): p. 2260-2274.
- 5. Nichter, B., et al., *Psychological burden of PTSD, depression, and their comorbidity in the U.S. veteran population: Suicidality, functioning, and service utilization.* J Affect Disord, 2019. **256**: p. 633-640.
- 6. Lamarche, L.J. and J. De Koninck, *Sleep disturbance in adults with posttraumatic stress disorder: a review.* J Clin Psychiatry, 2007. **68**(8): p. 1257-70.
- 7. Lanius, R.A., et al., *The dissociative subtype of posttraumatic stress disorder: rationale, clinical and neurobiological evidence, and implications.* Depress Anxiety, 2012. **29**(8): p. 701-8.
- 8. Lanius, R.A., et al., *Emotion modulation in PTSD: Clinical and neurobiological evidence for a dissociative subtype.* Am J Psychiatry, 2010. **167**(6): p. 640-7.
- 9. Nicholson, A.A., et al., *The Dissociative Subtype of Posttraumatic Stress Disorder: Unique Resting-State Functional Connectivity of Basolateral and Centromedial Amygdala Complexes.* Neuropsychopharmacology, 2015. **40**(10): p. 2317-26.
- 10. Hoge, C.W., et al., *Combat duty in Iraq and Afghanistan, mental health problems, and barriers to care.* N Engl J Med, 2004. **351**(1): p. 13-22.
- 11. Statement Of Jon A. Wooditch Acting Inspector General Department Of Veterans Affairs, in Committee On Veterans' Affairs Subcommittee On Disability Assistance And Memorial Affairs. 2005: Washington, DC.

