### **8.8.2 Analysis of Adverse Events**

The primary measure of safety will be the reporting of unsolicited AEs. All AEs collected from Enrollment to Termination will be categorized as follows:

- Pretreatment AEs are defined as AEs that occur during the Preparatory Period prior to the first dose in the first Experimental Session
- Treatment Emergent AEs are defined as AEs that occur during the Treatment Period from the first Experimental Session to the last Integrative Session
- AEs that occur on and two days after MDMA administration
- AESIs are defined as AEs specified in the protocol related to cardiac function and abuse liability
- Follow-up Period AEs are defined as AEs that occur during the Follow-up Period after the last Integrative Session through Termination
- AEs leading to discontinuation of IP
- AEs resulting in death or hospitalization.
- SAEs
- AEs continuing at Termination.

Verbatim terms on case report forms will be mapped to preferred terms (PT) and system organ class (SOC) using the Medical Dictionary for Regulatory Activities (MedDRA) Version 24.0. Frequency and incidence of AEs will be displayed by PT, sorted by SOC, severity, and seriousness. AEs will be analyzed and presented as follows:

- If a participant has more than one AE mapped to the same PT, that AE will be reported once using the highest severity
- Relationship will be determined by the Clinical Investigator
- AEs that occur on day of Experimental Sessions and two days after IP administration will be presented separately.

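### The AE timing items listed in the protocol are dates only, so session AEs can be reported only by calendar day and overnight AEs fall across two days

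*Protocol*

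**What the plan says.** Protocol section 10.1 introduces its list with "For each event, the following information will be recorded in the participant's record and transcribed into the AE section of the eCRF" and the SAE form where relevant. Two items on the list concern timing: "Event onset date. If a laboratory event is reported as an AE, record the start date as the date of collection" (the sentence goes on about laboratory samples) and "Event stop date: date the event resolved". No item gives a clock time, the relation to a dose, the phase of the session or the visit at which the event was reported.

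SAP section 8.2.1 imputes partial dates and has no rule for times. SAP section 8.8.2 plans that "AEs that occur on day of Experimental Sessions and two days after IP administration will be presented separately". Protocol section 13.2.2 and SAP section 8.8 use a Day 0, Day 1, Day 2 display and label Day 0 as the Experimental Session. A separate sentence then asks for the relative incidence of AEs during the sessions.

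Three uses of the data call for finer timing:

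- Safety objective 1 (protocol section 2.3, SAP section 3.3): "Assess incidence of AEs during Experimental Sessions that may be indicative of a medical complication of the Investigational Medicinal Product (IMP", followed by examples such as chest pain, shortness of breath and neurological symptoms.
- The split by treatment status in SAP section 8.8.2: "Pretreatment AEs are defined as AEs that occur during the Preparatory Period prior to the first dose in the first Experimental Session". Treatment Emergent AEs run from the first Experimental Session.
- Appendix A, on the sub-study without overnight stays: "case reports and AEs collected on the night of the Experimental Session will be evaluated to support feasibility". Its rationale also foresees pooling sub-study samples across trials for a safety comparison with participants who stayed overnight.

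**The concern.** MDMA effects are measured in hours. Protocol section 1.2.2 puts the effects of the initial dose at 3 to 6 hours. A calendar date cannot separate a complaint present on arrival, a reaction under the drug and an event late that evening. If the listed items are all that the analyst receives, the Day 0 column will be read as the acute-session profile although it holds all three kinds of event. A night event after a session may carry either of two dates, and each date also holds events from outside the night. The stated aim of the safety data is to support the package insert, so the acute profile is one of the outputs that readers will use most.

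**Working it through.** The documents give no figure on this point, so there is none to reproduce. The check sets the data items against the windows that the analyses need, and then uses the protocol's own clock to show how coarse a date is.

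**Inputs.** Dose at about 10:00 and last assessments at 17:30 (Table 7). Sessions last at least 6 hours, counted from 30 minutes before dosing (section 7.3.1), so the shortest session runs from 9:30 to 15:30. Three sessions per participant, with about 100 participants. The next-morning visit has no stated clock time; 09:00 is assumed, with a range of 08:00 to 11:00.

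**Day 0 against the session**

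- Before the dose: 10.0 h, and 10.0/24 = 41.7%.
- Dose to session end: 17.5 − 10.0 = 7.5 h, and 7.5/24 = 31.3%.
- Evening: 24 − 17.5 = 6.5 h, and 6.5/24 = 27.1%.
- Outside dose-to-session-end: 10.0 + 6.5 = 16.5 h, or 68.8%.
- Shortest session: 15.5 − 10.0 = 5.5 h dosed (22.9%), 24 − 15.5 = 8.5 h evening, and 24 − 5.5 = 18.5 h outside (77.1%).

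**The night against the calendar**

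- 17:30 to midnight is 6.5 h on Day 0; midnight to 09:00 is 9.0 h on Day 1; total 15.5 h.
- Day 1 share: 9.0/15.5 = 58.1%.
- Visit at 08:00: 8.0/14.5 = 55.2%. Visit at 11:00: 11.0/17.5 = 62.9%.

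The date therefore does not isolate the session, and neither date contains the night.

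**The Pretreatment cut.** The SAP cuts Pretreatment AEs at the first dose but starts Treatment Emergent AEs at the first session. Protocol section 7.3.1 has the site record AEs that morning before dosing. Such an event has the same onset date as an acute reaction, and the two definitions do not settle its class. The SAP's date imputation can add to the tie, because an AE with an unknown start day in the month of first dose is moved to the first-dose date. The tie arises on one date per participant, about 100 in all. After the first dose, everything up to the last Integrative Session is treatment emergent, so the mornings of sessions 2 and 3 are not affected.

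**Could a cut at session end replace the day?** No. Section 1.2.2 says that most effects are back at or near baseline 6 hours after the final dose. A supplemental dose at 11:30 to 12:00 (1.5 to 2 hours after 10:00) puts that at 17:30 to 18:00, after the shortest session has ended at 15:30. A session-end window used alone would drop drug effects that Day 0 keeps.

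**The case against.** The strongest reply is that the plan already gives a workable definition: it labels Day 0 as the Experimental Session, and AEs by day are coarse but reportable. This stands. A reader might infer that objective 1 cannot be derived at all, and the documents do not support that.

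Second, the eCRF and source templates are not among the documents. AEs are asked about before dosing, at the end of the session and the next morning, so the contact at which an event was reported may be captured. Source records document all procedures, and Table 7 starts video recording before the dose. A reader might infer that the timing is lost for good, but some of it may be recoverable case by case. What remains is that section 10.1 does not ask for the contact or the time, and the SAP has no rule that would use either.

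Third, the sub-study plans no formal analysis, and its review takes AEs collected that night together with case reports. That review can go ahead without a programmed time window. The gap bears more on the pooled comparison with overnight stays.

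Fourth, each AE carries a related or not-related judgement, so a Day 0 event is not automatically attributed to the drug. That is a partial safeguard. It is a judgement and does not place the event in time. Objective 1 is also limited to events that suggest a medical complication, so poor sleep or anxiety before the dose would largely fall outside it.

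**Conclusion.** The point holds as a gap in data collection with a matching gap in the SAP. From the items listed in section 10.1, AEs during sessions can be reported only as calendar Day 0, on up to 3 × 100 = 300 session days. The Pretreatment cut is a date tie on the Visit 4 date only. Night events are spread over Day 0 and Day 1.

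A reader might take the 69% to 77% of Day 0 that lies outside dose-to-session-end as an error rate. It is a share of clock hours. The documents give no distribution of AE onset over the day, so the share of events affected is unknown and could be much smaller. Evening events may also be genuine drug effects.

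The conclusion assumes that the eCRF follows the section 10.1 list and, for the night, that the next-morning visit falls between 08:00 and 11:00. If the eCRF already holds an onset time or the contact of collection, only the SAP rule is missing. No effectiveness result is affected.

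**What to change.** In protocol section 10.1, for AEs that start between arrival on a session day and the next-morning Integrative Session, record the onset time. If it is unknown, record a phase: pre-dose, initial dose to session end, or after the session and overnight.

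In SAP section 8.8.2, class same-day pre-dose AEs by time or phase instead of by date, including at Visit 4. Show in-session and overnight AEs as separate columns alongside the Day 0/1/2 display, and keep that display so that drug effects lasting past session end are not dropped.

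If no field is added, the SAP should at least say that AEs during a session means Day 0, and state how pre-dose AEs on the Visit 4 date are classed.

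The cost is one or two extra eCRF fields on session days, filled at contacts where staff already ask about AEs, and a few lines of SAP text. Some times will be approximate, which the phase option allows for.

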HIPAA Health Insurance Portability and Accountability

HIV Human Immunodeficiency Virus

HPA Hypothalamic-pituitary-adrenal HPMC Hydroxypropyl Methylcellulose

HPQSF Health and Work Performance Absenteeism and Presenteeism Short Form

IB Investigator's Brochure

ICD International Classification of Disease

ICF Informed Consent Form

ICH International Conference on Harmonisation

IND Investigational New Drug

IMP Investigational Medicinal Product

IR Independent Rater

IRB Institutional Review Board
ISF Investigator Site File
ITT Intent-to-Treat
IUD Intrauterine Device

IUS Intrauterine Hormone-releasing System IWRS Interactive Web Randomization System

kg Kilogram

LEC-5 Life Events Checklist LTFU Long-term Follow-up

MAPS Multidisciplinary Association for Psychedelic Studies

MAOI Monoamine Oxidase Inhibitor MCH Mean Corpuscular Hemoglobin

MCHC Mean Corpuscular Hemoglobin Concentration

MCV Mean Corpuscular Volume

MDMA 3,4-methylenedioxymethamphetamine MedDRA Medical Dictionary for Regulatory Activities

mg Milligram

MINI Mini-International Neuropsychiatric Interview

mITT Modified Intent-to-Treat mmHg Milligrams of Mercury

MMRM Mixed Model Repeated Measure MPBC MAPS Public Benefit Corporation

ms Millisecond

PABP Participant able to become pregnant

PCL-5 PTSD Checklist for DSM-5
PHI Protected Health Information
PTSD Posttraumatic Stress Disorder
PVC Premature Ventricular Contraction

RACT Risk Assessment and Categorization Tool

RBC Red Blood Cell

RDW Red Cell Distribution Width SAE Serious Adverse Event SDS Sheehan Disability Scale

SGOT Serum Glutamic Oxaloacetic Transaminase SNRI Serotonin-norepinephrine Reuptake Inhibitor

SRNU Self-reported Nicotine Use

SSRI Selective serotonin reuptake inhibitor
TEAE Treatment Emergent Adverse Event
TSH Thyroid-stimulating Hormone

UFEC Utilization of Facility-based and Emergent Care

U.S. United States

VA U.S. Department of Veterans Affairs

VAS Visual Analog Scale WBC White Blood Cell

WHO World Health Organization

1.0 Introduction

The Multidisciplinary Association for Psychedelic Studies (MAPS) is a non-profit research and educational organization working as a clinical trial sponsor to obtain marketing approval for the prescription use of 3,4-methylenedioxymethamphetamine (MDMA) as an adjunct to therapy in patients with posttraumatic stress disorder (PTSD). Controlled Phase 1 studies, nonclinical studies, and investigator-initiated studies formed the basis for the Clinical Development Program of MDMA under Investigational New Drug (IND) #063384. MAPS-sponsored studies are implemented through MAPS' wholly owned subsidiary and delegate, the MAPS Public Benefit Corporation (MPBC).

1.1 Rationale

PTSD is a serious debilitating disorder that negatively impacts a person's daily life. MDMA has been shown to reduce defenses and fear of emotional injury, enhance communication, and increase empathy. MDMA may enhance fear extinction learning in humans. These subjective effects of MDMA create a productive psychological state that enhances the therapeutic process for the treatment of PTSD and other anxiety disorders. This is supported by data from an international series of Phase 2 pilot studies of MDMA-assisted therapy conducted by the sponsor that provide preliminary evidence that chronic PTSD, independent of cause, is treatable with two to three sessions of MDMA-assisted therapy and associated non-drug preparatory and integrative therapy.

The results from multiple independent studies in Phase 2 efficacy analyses demonstrate superiority of MDMA-assisted therapy over therapy with placebo and low dose MDMA. The acceptable risk-benefit ratio in early trials justified confirmation in a Phase 3 program to further assess the efficacy and safety of this treatment for participants with at least moderate PTSD. The sponsor completed two Phase 3 randomized, placebo-controlled, two-arm, double-blind, multi-site studies of three once-monthly Experimental Sessions of therapy combined with either a flexible dose of MDMA or placebo, along with non-drug preparatory and integrative therapy.

Participants who were randomized to the placebo arm in either of the two parent Phase 3 trials and who meet all other entry criteria will be eligible and invited to participate in this open-label safety extension study. In addition, participants in the parent Phase 3 trials whose study participation was affected by the Coronavirus 2019 (COVID-19) global pandemic or other unforeseen circumstances and were unable to complete the study (enrolled but not treated or enrolled, treated, but could not complete three Experimental Sessions prior to termination of the study) may participate in this open-label study. This study will follow a similar schedule of events as the Phase 3 protocols but will measure PTSD severity using a self-report measure, the PTSD Checklist (for Diagnostic and Statistical Manual of Mental Disorders, 5th edition [DSM-5]) (PCL-5).

1.2 Background

1.2.1 PTSD

PTSD is a serious debilitating disorder associated with increased mortality and cardiometabolic morbidity. PTSD is a stress-related psychiatric condition that may occur following a traumatic event such as war, disaster, sexual abuse, violence, terrorism, and accidents [1]. The four main symptom categories described in the DSM-5, include arousal and reactivity, avoidance of triggers, negative thoughts and feelings, and intrusive thoughts and nightmares [2]. PTSD negatively impacts a person's daily life, resulting in fractured relationships, inability to maintain employment, diminished cognitive and psychosocial functioning, substance abuse, high-cost healthcare utilization, and increased depression and suicide risk [3-5]. People who suffer from PTSD often relive the experience through nightmares and

IND #063384

flashbacks, have poor sleep quality, and feel detached or estranged [6]. Confronting overwhelming internal distress and frightening external environments can also lead to high levels of depersonalization and derealization, which led clinicians to identify a dissociative subtype of PTSD in the DSM-5 [7]. Adaptations in normal brain function have been observed in imaging studies of patients with PTSD that underlie alterations in emotional processing and regulation, cognition, and many aspects of behavior, though clinical symptoms and changes in brain activity are not homogenous across patients [7]. The dissociative subtype occurs in 12 to 30% of people with PTSD and is characterized by detachment and emotional numbing and visualized in the brain as overmodulation of affect mediated by midline prefrontal inhibition of limbic regions, while the non-dissociative subtype presents symptoms of hyperarousal and re-experiencing, an emotional undermodulation mediated by failure of prefrontal inhibition of the same limbic regions [8, 9]. Patients suffering from the dissociative subtype of PTSD typically have early childhood trauma and appear to be particularly difficult to treat, with mixed response to existing evidence-based treatments.

Approximately 7% of the population in the United States (U.S.) will have PTSD sometime in their life, but this figure jumps to 10.8% to 13% of veterans with combat experience [10]. For soldiers returning from Iraq and Afghanistan, the incidence of PTSD is 17.1% with 400,000 to 500,000 U.S. Iraq/Afghanistan veterans reportedly having PTSD. In 2004, the Defense Department and U.S. Department of Veterans Affairs (VA) spent \$4.3 billion on PTSD disability payments to approximately 215,000 veterans [11]. In 2012 alone the VA spent \$294 million and \$3 billion, respectively, on care for veterans with the disorder and disability payments, even with this funding the demand for services far outreached the availability of VA doctors and services. As of June 30, 2016, more than 868,000 veterans with a diagnosis of PTSD were receiving disability compensation for service-connected mental disorders, with an estimated cost of about \$17 billion per year [12]. There are an estimated 20 to 22 suicides a day by veterans [13].

Available PTSD treatments, including medications and therapy, effectively treat only a fraction of people who try them for adequate dose and duration. This indicates a need to develop treatments targeting durable remission of PTSD. The Food and Drug Administration (FDA) has approved only two pharmacotherapies for PTSD, both of which are selective serotonin reuptake inhibitors (SSRIs). Paroxetine and sertraline (Paxil and Zoloft) both demonstrated statistically significant superiority over placebo on the Clinician Administered PTSD Scale (CAPS) in 12-week confirmatory clinical trials with daily dosing, but some studies were less effective in treating combat-related PTSD and sertraline demonstrated gender differences with minimal efficacy in men [14-16]. PTSD rarely remits after 12 weeks of SSRIs, and many patients who are placed on maintenance treatment experience partial relief of symptoms, which fully return upon discontinuation of treatment. Adverse effects of maintenance SSRI treatment that contribute to discontinuation include sexual dysfunction, weight gain, and sleep disturbance. Variable SSRI treatment outcomes have led to recommendations of trauma-focused psychotherapy as routine first-line treatment by the VA's National Center for PTSD in the U.S., as well as by the World Health Organization (WHO). An extensive list of medications, namely antipsychotics, anxiolytics, antidepressants, and sleep aids, are frequently prescribed off-label but have only small effect sizes in reducing PTSD symptoms. PTSD brings a high public burden, both economically and socially, by increased use of health and social services, lost wages, and disability payments [17, 18]. Given the chronicity of PTSD, low compliance evidenced by high dropouts, and limited recovery with current medications contributing to serious outcomes, PTSD patients suffer from unmet medical need.

One treatment approach is to develop medications and/or therapeutic treatments that may indirectly decrease or eliminate the neurochemical pathologies underlying the chronic hyperarousal and dysregulation of the hypothalamic-pituitary-adrenal (HPA) axis associated with PTSD. Cognitive behavioral therapies, particularly prolonged exposure and cognitive processing therapy, are considered among the most effective psychotherapies. Other methods such as psychodynamic therapy and eye

movement desensitization and reprocessing (EMDR) have also proven to be effective in treating some symptoms of PTSD [19, 20], although some patients may need more than one type of treatment to reduce or resolve those symptoms. A meta-analysis concluded that all "bona fide" psychotherapies, including those listed above, are similarly effective with PTSD [21]. In the past decade, there has been a growing amount of research into medications and other methods that may augment the effectiveness of psychotherapy for PTSD (see [22] for a review). Examples of this are virtual reality-assisted exposure therapy [23, 24] and D-cycloserine-assisted psychotherapy [25]. MDMA-assisted therapy is another such approach.

